### 7.1 Double-Blind Phase

All efficacy analyses will be conducted in the ITT population. A supportive analysis of the primary and secondary efficacy endpoints also will be conducted in the PP population.

The estimand that is most clinically relevant as well as estimable in a manner that protects the integrity of randomization is the outcome measure (e.g., the percent change in 28-day seizure frequency), where ALL randomized subjects would be included in this analysis throughout the study period. Hence, all available data will be used, even if they were collected after the subject stopped taking study medication, regardless of whether the subject took rescue medication. [Section 7.1.1](#) details the handling of missing data.

For the analyses of seizures, the baseline phase consists of 6 weeks before the first day of treatment and the DB phase starts the day following the first day of DB treatment until the final visit for subjects who do not enter the OLE and up to the day before the first dose of OLE treatment for those who do. The first day of treatment is not in either phase since the seizures could occur both before and after the first treatment.

Tests of significance between the 2 treatment groups will be performed for the primary endpoint with a 2-sided significance level of 0.05.

Seizure diary compliance for the baseline and the post-baseline DB phase intervals will be calculated as:

$100 \times (\text{Number of Days with Available Seizure Diary}) / (\text{Last Available Seizure Diary Date} - \text{First Day of the Phase} + 1)$ .

Seizure diary compliance between visits will be calculated as:

$100 \times (\text{Number of days with available seizure data between visits}) / \text{Number of days between visits}$ , with the days between visits defined as the day of the prior visit up to the day before the current visit.

The compliances will be summarized with descriptive statistics and the percentage of subjects at least 80% compliant.

### 7.1.1 Handling of Missing Data

The primary analysis will use all available data. Careful educating and monitoring of the study sites will attempt to limit the amount of missing data to nearly zero, but despite these efforts, some missing data may still arise. Thus a sensitivity analysis, in which the missing data will be replaced, will be performed on the primary efficacy endpoint; see [Section 7.1.8](#).

When an item from a secondary or efficacy endpoint is missing, then so will any subscales or totals that include it.

When subjects prematurely discontinue from the study they are asked to complete the non-seizure assessments at the Taper Visit. For analysis purposes, their data from the Taper Visit will be reassigned to the first visit at which the assessment is scheduled subsequent to the discontinuation and the scheduled day is within 32 days of the Taper visit. For example if a subject completed Visit 3 and then prematurely discontinued and completed assessments at the Taper Visit on Study Day 100, then the Taper visit would be reassigned to Visit 5 (Week 17) for analysis purposes since Visit 5 is scheduled for Study Day 120, 20 days after the assessments were actually completed. (Although the first visit after Visit 3 is Visit 4 (Week 9), that visit is scheduled on Study Day 64, which is not within 32 days of Study Day 100.) But if the Taper Visit assessments were completed on Study Day 28 then the Taper visit would not be reassigned to a regular study visit since Study Day 28 is not within the 32-day window of any scheduled visit. Taper Visit assessments that are not reassigned will not be included in the tabulations but will be included in the data listings.

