Participants will be required to complete a daily seizure calendar noting seizure type and frequency in an eDiary calendar to determine GNX’s effect on seizures. In rare cases when an eDiary completion is not feasible, a paper seizure calendar will be used to log in daily seizure type and frequency. These cases will need approval by the sponsor. A variety of clinician and caregiver administered instruments will be used to assess the efficacy of GNX in CDKL5, and included: Caregiver Global Impression of Change in Attention (CGICA), Caregiver Global Impression of Change (CGI-C) in parent/caregiver identified behavioral target- potential domains of sociability, communication, irritability, and hyperactivity, Clinical Global Impression of Improvement (CGI-I) by parent/caregiver and clinician, Caregiver Global Impression of Change in Seizure Intensity/Duration (CGI-CSID), Children’s Sleep Habit Questionnaire (CSHQ), ADAMS, QI-Disability, and PSI.

Safety and tolerability will be assessed by monitoring vital signs (blood pressure [BP], heart rate [HR], respiratory rate [RR], body temperature, weight, and height), ECGs, clinical laboratory tests (hematology, chemistry, and urinalysis), physical, neurological, and developmental examinations, and frequency, type, and severity of AEs during the 17-week, double-blind phase and the open-label phase.

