26) Child wakes up by him/herself (R)				Yes	No	N/A
27) Child wakes up in negative mood				Yes	No	N/A
28) Adults or siblings wake up child				Yes	No	N/A
29) Child has difficulty getting out of bed in the morning				Yes	No	N/A
30) Child takes a long time to become alert in the morning				Yes	No	N/A
31) Child seems tired				Yes	No	N/A

Child has appeared very sleepy or fallen asleep during the following (check all that apply):

	1 Not Sleepy	2 Very Sleepy	3 Falls Asleep
32) Watching TV			
33) Riding in car			

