10. Showed aggression (e.g. hitting, kicking, using offensive language, being destructive)					
11. Appeared upset or angry (e.g. crying, screaming, moving or stiffening the body)					
12. Become withdrawn with a low mood					
13. Deliberately hurt themselves					
14. Expressed discomfort with changes in routine (e.g. carers, school, respite, out-of-home care)					
15. Showed signs of being anxious or agitated (e.g. teeth grinding, fast breathing, avoidance)					

Family and friends

Over the past month, how often has your child...	Never	Rarely	Sometimes	Often	Very often
16. Expressed happiness when they were understood					
17. Appeared relaxed when making eye contact					
18. Initiated greetings with people verbally or nonverbally (e.g. eye contact)					
19. Enjoyed being included					
20. Enjoyed the social experiences of meal times					
21. Responded positively when others paid attention to them (e.g. your child smiled, showed interest)					

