32. Enjoyed using technology (e.g. computer, tablet, applications on phones)					

Comments: _____

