12.12. Appendix 12: Parenting Stress Index (PSI)

Tool 1: Parental Stress Scale (questionnaire attached)

Component being measured:

- Attempts to measure the levels of stress experienced by parents.
- Takes into account positive and negative aspects of parenting.

Why this outcome matters?

Higher levels of parental stress related to:

- Lower levels of parental sensitivity to the child
- Poorer child behaviour
- Lower quality of parent – child relationship.

In particular, provides evidence related to Children's Centres work to 'improve parenting' and Core Purpose goal of 'improving parenting skills'

Tool details:

- Developed by Berry and Jones (1995) as an alternative to the 101-item Parenting Stress Index.
- Provides a measure that considers positive aspects of parenting as well as the negative, 'stressful' aspects traditionally focused on.

Format of the tool:

- 18 – item self report scale – items represent positive (e.g. emotional benefits, personal development) and negative (demands on resources, restrictions) themes of parenthood.
- Respondents agree or disagree in terms of their typical relationship with their child or children
- 5 – Point scale; strongly disagree, disagree, undecided, agree, strongly agree.

Use of the tool:

What can the tool help to assess?

- Changes in parental stress levels for parents/carers who have accessed targeted support, such as family support, parenting courses and one to one parenting support.
- The outcomes of services or areas of work focused on improving parents/carers parenting capacity.

Practical administration:

- Self completion or could be administered as an interview.
- The scale is relatively short and easy to administer – can be completed in less than 10 minutes.
- Can be used as a before and after measure.

Scoring the tool :

We want a low score to signify a low level of stress, and a high score to signify a high level of stress.

Range of Validated quantitative tools and scales that can be used to measure the outcomes of children's centre work 2013 [1](#)

Parental Stress Scale

The following statements describe feelings and perceptions about the experience of being a parent. Think of each of the items in terms of how your relationship with your child or children typically is. Please indicate the degree to which you agree or disagree with the following items by placing the appropriate number in the space provided.

1 = Strongly disagree 2 = Disagree 3 = Undecided 4 = Agree 5 = Strongly agree

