## 2.5 Handling of Missing Data

Missing data will not be replaced except as noted. Missing efficacy data will be imputed in a sensitivity analysis as described in [Section 7.1.7](#).

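### One blank item voids every subscale or total that contains it, so nearly complete caregiver questionnaires drop out of the descriptive change scores

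*SAP*

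**What the plan says.** SAP section 7.1.1 gives the item-level rule: "When an item from a secondary or efficacy endpoint is missing, then so will any subscales or totals that include it". SAP section 2.5 gives the general position: "Missing data will not be replaced except as noted". In the visible text, the only replacement of missing efficacy values is in the sensitivity analyses of the primary seizure endpoint (SAP 7.1.8). On how much missingness to expect, SAP 7.1.1 says: "Careful educating and monitoring of the study sites will attempt to limit the amount of missing data to nearly zero". It then accepts that some may still occur.

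Protocol section 3.1 includes the four multi-item caregiver forms among the instruments used to assess efficacy: "Sleep Habit Questionnaire (CSHQ), ADAMS, QI-Disability, and PSI". On a plain reading the rule covers them. The SAP text that would describe their scoring, after section 7.1.3.4, is redacted.

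SAP section 7 summarises baseline, post-baseline and change-from-baseline values of the non-categorical endpoints, with 95% confidence intervals for means and differences in means. SAP section 2.1 defines the baseline of a non-seizure assessment as its last non-missing value before the first dose, and uses the same baseline in the open-label extension.

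**The concern.** The rule discards a form on which all but one answer was collected. A change score needs two complete forms, so the exposure doubles. The baseline form matters most. Protocol 7.2.1.2 (Screening) does not list the four questionnaires and 7.2.1.3 (Visit 2) does, so no earlier form can stand in. One blank at Visit 2 removes that subject's total change score, and that of any subscale containing the item, at Weeks 5, 9 and 17 and throughout the open-label phase.

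The rule is also out of step with the rest of the plan. SAP 7.1 argues for including all randomised subjects and all available data, with seizure frequency as its example. SAP 7.1.2 divides seizure counts by the number of days with diary data, which is prorating, and SAP 7.1.8 treats sporadic diary gaps as missing completely at random. A blank questionnaire item is the same kind of gap, handled in the opposite way without a stated reason. What is at stake is the precision of the questionnaire estimates in a trial of about 100 subjects.

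**Working it through.** The plan states no item-skip rate and no score-loss figure, so there is nothing of its own to reproduce. The skip rate q below is an assumption and is shown over a range.

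**Inputs from the protocol appendices.** The form headed Parenting Stress Index is the Parental Stress Scale, described as an "18 – item self report scale" (Appendix 12). ADAMS has 28 numbered items (Appendices 9 and 10). QI-Disability ends at item 32, "Enjoyed using technology (e.g. computer, tablet, applications on phones" (Appendix 11). The CSHQ ends at "33) Riding in car" (Appendix 8). I assume that each total uses every item on its form.

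**Formulas.** With k items and independent skips at rate q:

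- loss of a single-visit total = 1 − (1 − q)^k
- loss of a change score = 1 − (1 − q)^(2k)

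**Worked case, q = 1%.** Single visit: 1 − 0.99^18 = 16.5%; 1 − 0.99^28 = 24.5%; 1 − 0.99^32 = 27.5%; 1 − 0.99^33 = 28.2%. Change score: 1 − 0.99^36 = 30.4%; 1 − 0.99^56 = 43.0%; 1 − 0.99^64 = 47.4%; 1 − 0.99^66 = 48.5%.

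Loss of total change scores by assumed skip rate:

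| q | Stress scale (18) | ADAMS (28) | QI-Disability (32) | CSHQ (33) |
|---|---|---|---|---|
| 0.1% | 3.5% | 5.4% | 6.2% | 6.4% |
| 0.25% | 8.6% | 13.1% | 14.8% | 15.2% |
| 0.5% | 16.5% | 24.5% | 27.4% | 28.2% |
| 1% | 30.4% | 43.0% | 47.4% | 48.5% |
| 2% | 51.7% | 67.7% | 72.6% | 73.6% |

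**Clustering.** If blanks concentrate on some forms, fewer forms are affected at the same mean rate. In a beta-binomial model with mean m = 1% and intraclass correlation ρ, P(no blank among n items) = B(a, b + n)/B(a, b), where s = 1/ρ − 1, a = ms and b = (1 − m)s. With the two visits independent, change-score loss from 18 to 33 items is 28.4–43.7% (ρ = 0.01), 22.8–32.3% (ρ = 0.05) and 18.6–24.9% (ρ = 0.10). If the same caregivers skip at both visits, it is 18.6–25.1% (ρ = 0.05) and 13.9–17.8% (ρ = 0.10).

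**Subscales.** Subscale lengths are not visible. For assumed lengths of 5 to 7 items at q = 1%: 1 − 0.99^10 = 9.6% and 1 − 0.99^14 = 13.1%.

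**Effect on precision.** If the losses are unrelated to outcome, standard errors grow by 1/√(1 − loss). At independent 1% this is 1/√0.696 = 1.20 for the stress scale and 1/√0.515 = 1.39 for the CSHQ. At 0.1% it is 1/√0.965 = 1.02 and 1/√0.936 = 1.03.

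**With prorating at 80% of items.** A form is lost only with at least 4 blanks of 18, 6 of 28, or 7 of 32 or 33. At independent q = 1%, change-score loss falls below 0.01% for all four totals. For 5- and 7-item subscales, where one blank is tolerated, it is 0.2% and 0.4%.

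**The case against.** The strongest objection is to the stronger reading. A reader might infer that blanks are bound to occur in the most impaired children, because items on sleepwalking, talking in sleep or aggression do not fit them, and that the analysed set is therefore biased. The forms do not support this. Each frequency scale has a valid answer for something that does not happen: *Rarely* on the CSHQ covers never, 0 on ADAMS covers behaviour that has not occurred, and QI-Disability has a *Never* column. The item "Showed aggression (e.g. hitting, kicking, using offensive language, being destructive" mentions language only as one bracketed example. The stress scale asks about the parent. Some blanks remain plausible, but selective loss is not shown.

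A reader might also take 30 to 48% as the expected loss. It is not. The 1% rate has no source in the documents, the SAP aims for almost no missing data, and Protocol 9.2 provides for checks for omissions and queries. Independence also puts the figure near the top of what a 1% rate implies. Single-visit summaries need only one complete form.

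Three further points stand as limits. The scoring text is redacted and may contain a partial-scoring rule, so its absence can be claimed only for the visible text. The questionnaires are not among the visible primary or secondary endpoints, and SAP 7.1.7 reserves formal testing for the primary. Prorating is itself an assumption: a skipped item whose true answer is *Rarely* would be replaced by the mean of the answered items, which may be higher.

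None of this gives a reason to discard a form with one blank. Prespecifying the rule and applying it equally to both arms makes it transparent but recovers no lost data.

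**Conclusion.** The point holds as a modest one. As visibly written, SAP 7.1.1 discards nearly complete questionnaires, and a blank at Visit 2 has lasting effect. The size depends on a skip rate that the documents do not give. Under independent skips, total change-score loss is about 4–6% at 0.1%, 17–28% at 0.5% and 30–48% at 1%. At 1% it falls to about 19–32% with intraclass correlation of 0.05–0.10 and independent visits, and lower if the same caregivers skip at both; it is about 10–13% for assumed 5- to 7-item subscales.

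The consequence is wider intervals on descriptive scores. The primary endpoint, the key secondary endpoints (responder rate and CGI-I) and the other single-rating CGI scales have no multi-item totals and are unaffected. Neither bias towards less impaired children nor any threat to the trial's main conclusion follows from the documents.

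**What to change.** Replace the sentence in SAP 7.1.1 with a rule such as: unless the instrument's own scoring rule specifies otherwise, reverse-score items where required; if at least 80% of the items of a subscale or total are answered, score it as the mean of the answered items multiplied by the number of items; otherwise set it to missing. Report the complete-item score as a sensitivity check, and tabulate the number of blank items per form and visit by arm so that the actual skip rate is known.

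Reverse-scoring must come first because the CSHQ marks (R) items and the stress scale mixes positive and negative statements. The 80% threshold is a judgement, not a figure from the documents. If the redacted text already contains instrument-specific rules, a cross-reference from 7.1.1 is enough.

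The cost is one SAP sentence and minor programming, settled before unblinding, plus a mild assumption that skipped items resemble the subject's answered items. The complete-item analysis shows whether that assumption matters.

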### 7.1.2 Primary Efficacy Endpoint

The primary efficacy endpoint is the percent change from baseline in 28-day primary seizure frequency during the 17-week DB treatment phase. Primary seizure types include bilateral tonic, generalized tonic-clonic, atonic/drop, bilateral clonic, or focal to bilateral tonic-clonic seizures. Post-baseline 28-day seizure frequency will be calculated as the total number of seizures in the 17-week DB treatment phase divided by the number of days with seizure data in the phase, multiplied by 28. Baseline 28-day seizure frequency will be calculated as the total number of seizures in the baseline phase divided by the number of days with seizure data in the phase,

multiplied by 28. The calculation for percent change from baseline in 28-day seizure frequency will be done as follows for each subject:

$$\left( \frac{[(\text{Post-baseline 28-day seizure frequency}) - (\text{Baseline 28-day seizure frequency})]}{(\text{Baseline 28-day seizure frequency})} \right) \times 100\%$$

The baseline and post-baseline values and the changes and percent changes from baseline in 28-day seizure frequency will be summarized using descriptive statistics.

The difference between the treatment groups in the percent changes from baseline will be tested for statistical significance. Since the percent differences are anticipated to display skewness and/or outliers, the tests will be performed using the Wilcoxon Rank-Sum statistic.

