6.2.2. Allocation of Subjects to Treatment

Subjects will be randomly assigned at a 1:1 ratio (GNX: PBO) based on a randomization schedule at Visit 2 (Week 0). Subjects will be stratified into 2 groups based on baseline seizure frequency. Only the investigational product supplier and the sponsor's investigational product manager will be unblinded as to the contents of each bottle of investigational product. Study staff as well as subject and caregiver will be blinded to treatment assignments.

An IWRS will centrally randomize subjects. The randomization schedule will be generated using a standard, validated method and maintained by the investigational product supplier and IWRS vendor. The investigator will be instructed by the IWRS, which numbered bottle to use to dose a subject. The investigator and research staff will be aware of the ascending dose design of the clinical investigation; however, the investigator, the research staff, and the subjects will be blinded with respect to who is receiving active drug versus PBO. The maximum PBO period is 17 weeks.

The contents of each bottle will be blinded using labels. The randomization schedule will match a subject number to a bottle number. Upon completion of baseline evaluations for each subject, the investigator or appropriate designee will log into the IWRS to receive a bottle number. Complete instructions for obtaining a bottle number will be provided to the clinical sites prior to initiating the study. The designated personnel at the clinical site will match the assigned bottle number with the correct bottle of investigational product and distribute the bottle to the investigator or designee.

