9.7.1. Primary Efficacy Endpoint

The primary efficacy endpoint is the percent change in 28-day primary seizure frequency through the end of the 17-week, double-blind treatment phase relative to the 6-week prospective baseline period. The primary seizure types include bilateral tonic (sustained motor activity ≥ 3 seconds), generalized tonic-clonic, bilateral clonic, atonic/drop seizures or focal to bilateral tonic-clonic.

The baseline, post-baseline, and arithmetic and percent changes from baseline in 28-day seizure frequency will be summarized using descriptive statistics. The difference between the treatment groups in the percent changes will be tested for statistical significance. Since the percent differences are anticipated to display skewness and/or outliers, the test will be performed using the Wilcoxon Rank-Sum statistic using a 2-sided significance level of 0.05.

Three sensitivity analyses of the primary efficacy endpoint will be performed (1) To examine the primary outcome measure when a subject stops recording measurements permanently prior to the end of the 17-week DB phase using the imputation approach outlined in the Statistical Analysis Plan, (2) to explore the possibility that subjects who stop recording seizure counts tend to have higher counts than other subjects, and (3) To examine the effect of GNX compared to PBO among subjects with low Allo-S levels.

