## 7. EFFICACY ANALYSES

In addition to the descriptive statistics mentioned in [Section 2.1](#), the baseline, post-baseline, and relevant changes from baseline for the seizure endpoints will also be summarized with 95% distribution-free confidence intervals for the median and Hodges-Lehmann point estimates and asymptotic 95% confidence limits for the location shifts. [Section 12.2](#) contains SAS code for obtaining the distribution-free confidence limits for the median and the Hodges-Lehmann estimates and confidence intervals.

The baseline, post-baseline, and changes from baseline for the other non-categorical endpoints will be summarized with 95% confidence intervals for the means and differences in means between the treatment groups in addition to the other descriptive statistics.

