### **7.1.8 Sensitivity Analyses**

Three sensitivity analyses of the primary efficacy endpoint of change in 28-day frequency of the primary seizure types will be performed:

Intermittent (random/sporadic) missing data during the 17-week DB phase and any missing data during the baseline phase will be assumed missing completely at random and the collected data will be used to calculate the 28-day seizure frequencies. For early drug termination prior to the end of the 17-week DB phase, caregivers will be instructed to continue to provide daily seizure records until the end of the 17-week DB phase (hence further preventing missingness).

In the first sensitivity analysis, the following imputation approach will be used for the primary outcome measure when a subject stops recording measurements permanently (anticipated to be

minimal in occurrence) prior to the end of the 17-week DB phase: for those missing days, the corresponding median PBO data will be imputed (irrespective of treatment arm) as follows:

- Partition the subjects in the PBO arm into quartiles, where the quartile equals  $\text{Floor}[\text{Rank} \cdot 4 / (n + 1)]$ , where  $\text{Floor}[\cdot]$  is the integer floor function, Rank is the rank of the 28-day seizure frequency in the PBO arm based on all available PBO measurements during the 6-week baseline phase (tied scores receive tied ranks), and n is the number of subjects in the PBO arm.
- Assign each subject for whom imputation is needed into the quartile that covers the 28-day seizure frequency based on that subject's available measurements during the 6-week baseline phase. If a frequency is lower than the lower bound of the lowest quartile (which could happen only in the GNX arm), then assign that subject to the lowest frequency quartile; likewise if a frequency is higher than the upper bound of the highest quartile, then assign that subject to the highest frequency quartile. If a frequency falls between two quartiles (which, again, could happen only in the GNX arm), then based on the distances between the frequency and the upper and lower bounds of the lower and higher quartiles, respectively, assign the subject to the closer quartile (in case of a tie, assign to the lower quartile).

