## 10. INTERIM ANALYSES AND DATA AND MONITORING COMMITTEE (DMC)

Up to two formal interim analyses are planned, in addition to the final analysis, of treatment effect on the primary endpoint. They will be conducted when 50 subjects and 75 subjects are at least 17 weeks post randomization. The interim analyses will include only those subjects, and will be based on use of O'Brien-Fleming monitoring boundaries regarding benefit and lack of benefit. If the trial is not terminated at the interim analyses, the sample size at the final analysis will be approximately 100 participants.

(Note that while the boundaries discussed in the remainder of this section will be illustrated for the setting in which 50 (75) subjects would be at least 17 weeks post randomization at the interim analysis, these boundaries will be computed based on the actual number 'X' of subjects at the times of the interim analyses.)

In addition, two supportive analyses will be performed, for informational purposes only, at each interim analysis:

- For those subjects who stop recording measurements permanently (anticipated to be minimal in occurrence) prior to the end of the 17-week DB phase, the imputation procedure for the first sensitivity analysis described in [Section 7.1.8](#) will be applied.
- All randomized subjects who are at least 4 weeks post randomization at the time of the interim analyses will be included.

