### 10.1 Termination Based on Reliable Evidence of Lack of Benefit

An O'Brien-Fleming boundary that rules out benefit will be used, protecting an experimental (one-sided) 0.025 false negative error rate, under an assumed maximum sample size of 100 participants, and under the alternative hypothesis that the percent change in 28-day seizure frequency on ganaxolone minus that on placebo truly is 0.5618 times the standard deviation for the percent change in 28-day seizure frequency; when that standard deviation is 44.5, this alternative hypothesis for the percent change in 28-day seizure frequency on ganaxolone minus

that on placebo would be 25%. (This reduction is the effect the trial has 80% power to detect at the final analysis when 100 subjects have completed their 17-week DB treatment phase.)

If the standard deviation for the percent change in 28-day seizure frequency is 44.5, then the estimate of the percent change in 28-day seizure frequency on ganaxolone minus that on placebo that would be at the boundary for early termination due to lack of benefit at 50 subjects would be approximately an estimated 10% increase, and at 75 subjects would be approximately an estimated 1% decrease.

The proposed boundary for termination based on reliable evidence of lack of benefit is somewhat conservative, in part due to the recognition that statistical significance might not be required for this trial to be sufficiently favorable to justify regulatory approval.

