## 12.2 SAS Procedures for Seizure Analyses

The following code will provide the 95% distribution-free confidence interval of the median:

```
proc univariate data=dataset(where=(specify analysis population,  
  endpoint, study phase, and time point) ciquandf;  
  class trtp; *trtp is the name of the randomized treatment  
    variable;  
  var pchg; *pchg is the name of the percent change variable;  
run;
```

The following code will provide the Wilcoxon rank-sum test along with the Hodges-Lehmann estimate and its asymptotic 95% confidence interval:

```
proc npar1way data=dataset (where=(specify analysis population,  
  endpoint, study phase, and time point) wilcoxon  
  HL(refclass='formatted value of PBO group');  
  class trtp; *trtp is the name of the randomized treatment  
    variable;  
  var pchg; *pchg is the name of the percent change variable;  
run;
```

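### Randomisation is stratified by baseline seizure frequency but the primary Wilcoxon test ignores the stratum: the plan is valid, and a stratified test is a cheap, optional refinement worth at most a few points of power

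*SAP*

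**What the plan says.** **Design.** Protocol 6.2.2: "Subjects will be stratified into 2 groups based on baseline seizure frequency". The cut-off and the expected stratum sizes are not given.

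**Primary test.** Protocol 9.7.1: "the test will be performed using the Wilcoxon Rank-Sum statistic using a 2-sided significance level of 0.05". SAP 7.1.2: "the tests will be performed using the Wilcoxon Rank-Sum statistic". Neither names a stratum or covariate.

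**Estimate.** SAP 7 adds "Hodges-Lehmann point estimates and asymptotic 95% confidence limits for the location shifts", again by treatment only.

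**Code.** SAP 12.2 introduces its program with "The following code will provide the Wilcoxon rank-sum test along with the Hodges-Lehmann estimate and its asymptotic 95% confidence interval". The only class variable is treatment, and there is no STRATA statement.

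**Other uses of baseline frequency in the visible text.** It is the denominator of the endpoint (SAP 7.1.2), it is summarised descriptively, and it forms the imputation groups in SAP 7.1.8 ("Partition the subjects in the PBO arm into quartiles"). None of these brings the randomisation stratum into the comparison of arms.

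**Sensitivity and interim analyses.** SAP 7.1.8 concerns the primary endpoint, and so does SAP 10: "Up to two formal interim analyses are planned, in addition to the final analysis, of treatment effect on the primary endpoint". Neither names a different test, so both are naturally read as using the unstratified one.

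**The concern.** Stratified randomisation balances the arms on the stratum. If the stratum also predicts the outcome, the true sampling variance of the treatment comparison is smaller than the variance an unstratified test assumes. The test then rejects too rarely under the null, its interval is slightly too wide, and some power is lost. With about 50 subjects per arm and one formal hypothesis test, it is fair to ask how much is given up by not analysing along the lines on which the trial was randomised.

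**Working it through.** **Inputs from the documents.** SD 44.5, effect 30 points, 100 subjects 1:1, one-sided 2.5% (SAP 1.3.2, protocol 9.5). Effect of 25 points: "This reduction is the effect the trial has 80% power to detect at the final analysis" (SAP 10.1). Final two-sided level about 0.048, interim boundaries Z = 3.73 at 50 subjects and 3.03 at 75 (SAP 10.2).

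**Reproducing the plan's power.** SE = 44.5 × √(2/50) = 8.9. Power at 30 points = Φ(30/8.9 − 1.96) = Φ(1.411) = 92.1%, against the stated 92%. The threshold is 1.96 × 8.9 = 17.4, against the stated 17.5 or so. The 92% is the ANOVA figure. The planned Wilcoxon test on the same normal data has about 90% (90.3% simulated; 90.9% from its asymptotic efficiency of 3/π).

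**Assumed, because the documents are silent.** Normal data, marginal SD held at 44.5, two equal strata balanced 1:1, and stratum means 0 to 30 points apart. With a gap g, the share of variance explained by the stratum is R² = 0.25g²/44.5². For g = 30 this is 225/1980.25 = 0.114, and the within-stratum SD is √(1980.25 − 225) = 41.9.

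**Normal-theory check at g = 30.** √(1 − R²) = 0.9415.

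- Unstratified type I error: 2Φ(−1.96/0.9415) = 2Φ(−2.082) = 3.7%.
- Power at 30 points: unstratified Φ(1.411/0.9415) = 93.3%; stratified Φ(3.371/0.9415 − 1.96) = 94.7%. Gain 1.4 points.
- Power at 25 points: unstratified Φ(0.849/0.9415) = 81.6%; stratified Φ(2.809/0.9415 − 1.96) = 84.7%. Gain 3.1 points.

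**Rank tests, simulated.** 40,000 trials per setting.

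- Unstratified: Z = (W − 2525)/√(50·50·101/12).
- van Elteren: Z = Σ w_k(W_k − m_k(N_k+1)/2) / √(Σ w_k² m_k n_k(N_k+1)/12), with w_k = 1/(N_k+1).

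Each cell shows unstratified vs van Elteren at two-sided 0.05:

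| Gap | Type I error | Power, 30 points | Power, 25 points |
|---|---|---|---|
| 0 | 4.8% vs 4.9% | 90.3% vs 90.2% | 77.7% vs 77.4% |
| 10 | 4.8% vs 5.0% | 90.3% vs 90.5% | 77.6% vs 77.6% |
| 20 | 4.4% vs 5.1% | 90.7% vs 91.5% | 77.8% vs 79.2% |
| 30 | 3.6% vs 4.9% | 91.5% vs 93.2% | 78.6% vs 81.9% |

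Monte Carlo standard error is about 0.11 points for type I error and 0.15 to 0.24 for power. Repeat runs put the bottom-left figure at 3.6% to 3.8%. The largest gains are 93.2 − 91.5 = 1.7 points and 81.9 − 78.6 = 3.3 points.

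**At the final level of 0.048 (critical value 1.977).** With no stratum effect, power is 90.0% vs 89.6% at 30 points and 76.7% vs 76.0% at 25, so stratifying loses 0.4 and 0.7 points. At a gap of 10 it can still be slightly behind (90.2% vs 89.9%; 77.4% vs 77.1%). The two tests draw level at a gap of about 10 to 15 points.

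**Interim looks, 30-point effect, no stratum effect.** Chance of crossing the benefit boundary: 4.5% vs 4.3% at 50 subjects and 38.0% vs 37.0% at 75.

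**Interval width.** The Hodges-Lehmann 95% interval is 36.4 vs 36.3 points wide with equal strata and 36.4 vs 34.1 with a gap of 30.

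**Departures from the assumptions.**

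- With a 30/70 split and a gap of 30: 91.4% vs 92.7% at 30 points, 78.5% vs 81.2% at 25.
- With skewed data (lognormal, sigma 0.5), 25-point effect and a gap of 30: 90.7% vs 94.8%.
- If the stratum acts only through regression to the mean (an assumed count model, with stratum medians 5 to 18 points apart), the gain is −0.1 to 0.5 points, within simulation error.

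**The case against.** The strongest reply is that nothing here is wrong. Stratifying for balance and then applying a simple prespecified rank test is legitimate, and neither document promises a stratified analysis. Baseline frequency already enters as the endpoint's denominator, so the two-level stratum may explain little of the percent change. In the one model that gives a mechanism, regression to the mean, the gain is close to nil. No assumed gap is taken from the documents, and if the strata do not matter a stratified test loses a little power. Parts of the SAP's efficacy section are blacked out, so an adjusted exploratory analysis cannot be excluded. All of this stands. It limits the point to an option without removing it: the visible primary test, estimate and code do leave out the randomisation stratum.

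A reader might infer that leaving out the stratum invalidates the test or inflates false positives. The error runs the other way: type I error stays at or below nominal. A reader might also infer that the trial is underpowered or that the 92% is wrong. The ANOVA figure reproduces, and SAP 1.3.2 says only that the Wilcoxon test has approximately the same power, which about 90% is consistent with.

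**Conclusion.** The mismatch between design and analysis is real, and its consequence is small. The planned test is valid, and conservative to the extent that the stratum predicts percent change. Over assumed gaps of 0 to 30 points, stratifying moves power by about −0.4 to +1.7 points at a 30-point effect and −0.7 to +3.3 points at a 25-point effect. The losses are at the final level of 0.048 with no stratum effect; the gains are at 0.05 with a 30-point gap. These figures rest on normal data, SD 44.5 and equal, balanced strata. The gain could be larger if the stratum explained more than the roughly 11% of variance that a 30-point gap implies, or with skewed data at that gap. The documents support no particular gap, so a claim of substantial lost power cannot be made from them. The change is optional.

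**What to change.** Before the unblinded primary analysis, and before any formal interim look if none has yet occurred (the documents do not show trial status):

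1. Make the primary test the van Elteren test, using the stratum recorded in the IWRS at randomisation.
2. Add a STRATA statement to the SAP 12.2 code.
3. Report a stratum-adjusted Hodges-Lehmann shift: the weighted median of within-stratum GNX-minus-PBO differences, weights 1/(n_k+1), with a 95% interval from inverting the stratified test.
4. State that the sensitivity and interim analyses use the same test.
5. Align protocol 9.5, 9.7.1 and the synopsis. SAP 11 gives the SAP precedence, but the discrepancy would otherwise remain.

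If the sponsor will not change the primary test, prespecify the van Elteren test as a supportive analysis. That needs a sentence or two and one extra SAS step.

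**Cost.** If the strata do not matter, the full change loses up to about 0.7 points of power at 100 subjects and about 1 point of interim crossing probability. It also needs the matching protocol wording and a short custom routine for the interval. No new data should be needed, since the stratum is required to randomise.
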